The trial is appropriately registered on clinicaltrials.gov under an Investigational New Drug (IND) number (IND 126491). **Treatment Randomization:** A permuted-block randomization list was developed by an independent statistician and retained by a research pharmacist at the study site. These two staff members were independent from those involved with the conduct of the study. The pharmacist uses the list to assign subjects to treatments. **Blinding.** The study supplements are administered by the pharmacist in a blinded fashion during the study so that the patient and clinical site personnel are not aware of the patient's assigned treatment. **Treatment side effects and unblinding:** All vitamin D levels and calcium levels are reviewed by the study medical monitor ([name]) at baseline and at three months (study completion). [name] is notified if vitamin D levels are greater than 100 ng/ml or if they experience hypercalcemia. In that case, patients are requested to return for repeat labs within one month of stopping therapy for monitoring purposes.

Sample Enrollment Criteria

A. Enrollment Criteria. Inclusion: 1) Women and men aged 18 to 75 years, 2) Having type 2 diabetes, 3) Having a subjective complaint of a cognitive dysfunction or scoring at least one standard deviation below normal on a cognitive functioning screening test (see Procedures and Measures), 4) Vitamin D level as measured by 25-hydroxyvitamin D (25-

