Questionnaire 9 tool (9 items). If the patient answers positively to item #9 on this tool which reads, “thoughts that you would be better off dead or hurting yourself in some way,” then he or she will be assessed for active suicide ideation using a form that is approved for suicidal ideation in the Sunshine Study 2 Protocol (see attached form). If the patient has active suicidal ideation, [name], psychiatrist will be contacted. If the patient has active suicidal ideation and is deemed to be in need of immediate psychiatric care, a member of the research team will escort the patient to the emergency room. In addition, the patient will be given a list of mental health resources and the patient will not be eligible to participate in the study. The baseline visit will be completed with collection of vital signs and a nursing physical assessment administered by a qualified member of the research team. The total amount of time for the baseline visit will be 2-3 hours. Once enrollment criteria have been met, **the second baseline visit** with a qualified member of the research team will be scheduled to dispense the Vitamin D supplement to the participant. At this visit, the six cognitive functioning tests will be administered again in order to wash-out any practice effects. The weekly medication administration schedule and all subsequent contacts (phone and scheduled visits) will be reviewed. Participants will be informed that, at three months, they will return for physical measurements and evaluation of cognitive functioning and self-care behavior. They will be told that in six weeks a qualified member of the research team will conduct a formal phone call follow-up, where they will be asked about medication compliance and side effects and screening for cognitive function using the Controlled Oral Word Association Test and Animal Naming Test. Upon completion of these verbal and written instructions and a negative pregnancy test (if necessary), the patient will be provided with the randomized vitamin D₃ medication. Following dispensing directions, a qualified member of the research team will ask the subject if they have any questions. The second visit will take two hours or less. At their **three-month visit**, the exact protocol from baseline visit (labs, questionnaires, and cognitive functioning tests) will be followed. The three month visit will take 3 hours or less. A qualified member of the research team will request the study medication bottle to estimate drug accountability by counting any remaining pills. **To forestall attrition and enhance compliance**, we will capitalize on retention strategies that have proven successful in [name] current NIH study (RO1NR013906), which include free parking and compensation for participants’ time. Participants will be compensated in a stepped manner: (\$20 at first baseline visit, \$25 at second baseline visit, and \$30 for completing the study at the three month visit). After the patients have completed the study, a letter (see attached letter) will be sent to them which includes the results of their HbA1c and Vitamin D levels.

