
Table 1: Scheduled Activities

	Screening	Week 0	Week 2	Week 8	Week 13
Depression Screen	X				
Demographics	X	X		X	X
Cognitive Tests	X	X	X	X	X
Questionnaires		X			X
Vitals		X			X
General Nursing Physical		X			

Blood Draw		X			X
Adverse Event Log		X	X	X	X
Dose Management Log			X	X	X
Concomitant Medication Log		X	X	X	X

4. Measurements.

A. Labs will be measured for each time point by Quest Laboratories which is accredited by the College of American Pathologists (CAP) and Clinical Laboratory Improvement Amendments (CLIA). **Serum vitamin D** will be measured by liquid chromatography/tandem mass spectrometry (LC-MS/MS) which is the standard for the measurement of vitamin D and its components. This method provides a total 25 hydroxyvitamin D (25 OH- D) which includes 25 (OH) D₂ and 25 (OH) D₃. Thus, we will be able to determine the effectiveness of vitamin D₃ supplementation. **Calcium** will be measured using a cardiometabolic profile. The **hemoglobin A1c** will be assessed using the DCA analyzer which is the practice in our diabetes center. Also, inflammatory markers will be collected. Potential confounders for vitamin D include sun exposure and diet and will be measured as follows: **(1) Sun Exposure:** Season of study enrollment will also be recorded and the Cancer Sun Exposure Tool which is 14 items and assesses sun exposure and use of sunscreen (35), **(2) Dietary Intake:** The Block Calcium and Vitamin D Screener will be used. This tool was developed from the NHANES 1999-2001 dietary recall data. It includes 19 food items, 3 supplement questions, and questions to adjust for food fortification practices (36).

B. Self-Management measures include: **(1) Diabetes Self-Care Inventory** (15 items) assesses a patient's perceptions of the degree to which they adhere to treatment recommendations for diabetes self-care (1= never do it to 5= always do it). This tool does not presume that all individuals have the same treatment prescription and thus is able to assess adherence to different treatment regimens (e.g., insulin or not taking insulin) (37, 38). **(2) Diabetes-Related Distress** (PAIDS, 20 items) measures the current burden of diabetes and its treatment. The responsiveness of the tool to detect changes in distress has also been established using data from seven prospective diabetes intervention studies (39).

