The research team will specifically review (1) number (if any) patients who develop vitamin D levels greater than 100 ng/mL or symptoms of vitamin D toxicity, (2) number (if any) patients who developed hypercalcemia, (3) number of patients (if any) who develop systolic blood pressure readings >160 mmHg or diastolic >100 mmHg, (4) number of patients (if any) who develop an increase in creatinine of 25% or more, and (5) patients with significant worsening cognition.

Individual Stopping Criteria

The research team will review data related to individual stopping criteria, as detailed below. The medical monitor may recommend modifications to individual stopping rules if additional safety concerns arise during their continuing review of the study data.

- If Vitamin D levels exceed 100 ng/mL at any time
- If a participant's CA >10.5 at any point
- If a participant develops a kidney stone
- Significant worsening cognition

Worsening cognition will be treated as an adverse event. Participants will be referred to an appropriate healthcare provider (i.e. Neuropsychologist, Clinical Psychologist, Psychiatrist, or Neurologist) by a member of the research team.

Study Stopping Criteria

The medical monitor may recommend stopping the study for the following reasons:

- The data show a significantly increased risk of serious adverse effects deemed related to the study supplement in one of the treatment groups
- It becomes clear that successful completion of the study is not feasible (e.g. there is an excess of patient dropout, missing data, lack of recruitment, etc)

In addition, termination or modification may be recommended for any other perceived safety concern based on clinical judgment, including but not limited to a higher than anticipated rate for any component of the primary endpoint, protocol failures resulting in adverse events, or unexpected adverse events.

Analysis Plan

Statistical Methods: Power

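### Once dosing has started, the vitamin D and calcium stopping rules have no scheduled blood result that could stop it

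*Combined protocol and SAP*

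**What the plan says.** Individual Stopping Criteria lists four rules. Two depend on a laboratory value: "If Vitamin D levels exceed 100 ng/mL at any time" and "CA >10.5 at any point". The other two, a kidney stone and a marked decline in cognition, do not.

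The blood schedule appears in three places:

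- The Blood Draw row of "Table 1: Scheduled Activities" is marked at week 0 and week 13 only.
- Study Design, under treatment side effects and unblinding, has the medical monitor review vitamin D and calcium "at baseline and at three months (study completion" and no further time. If a limit is passed, "patients are requested to return for repeat labs within one month of stopping therapy for monitoring purposes".
- Study Procedures puts the first draw at the first baseline visit. The supplement is handed out at a later, second baseline visit. After that, "in six weeks a qualified member of the research team will conduct a formal phone call follow-up", covering compliance, side effects and two verbal fluency tests. Blood is drawn again at the three-month visit, where the team "will request the study medication bottle to estimate drug accountability by counting any remaining pills".

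**The concern.** The wording of the two laboratory rules suggests continuous protection: a participant whose calcium or vitamin D goes too high will be taken off the supplement. The protocol itself treats the hazard as real. It excludes people with hypercalcemia because vitamin D can raise calcium, and it ties the calcium measurement to starting the 50,000 IU dose. If no result is available while supplement remains to be taken, a participant whose calcium rises early and without symptoms takes every remaining dose, and the limit is first checked at the end. An ethics committee or medical monitor reading the stopping criteria would not expect that. What is at stake is participant safety and the accuracy of the safety plan.

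**Working it through.** The plan gives no figure for this point, so the check sets the schedule beside the rules and counts. The stated power of 81.1% is not an input.

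**1. Schedule against dosing** (Table 1 and Study Procedures)

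| Time | Contact | Blood | Dosing |
|---|---|---|---|
| Week 0 | First baseline visit | Yes | Not started |
| Week 2 | Second baseline visit, supplement dispensed | No | Starts |
| Week 8 | Phone call, six weeks after dispensing | No | Under way |
| Week 13 | Three-month visit, bottle requested | Yes | Study completion |

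Draws after the first dose and before the final visit: 0.

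**2. Can either scheduled draw stop dosing?** The week 0 draw works as an eligibility screen. Enrollment requires 25-OH D below 32 ng/mL and excludes hypercalcemia. The week 13 draw coincides with completion. The sentence "Labs will be measured for each time point by Quest Laboratories" does not add a draw: it introduces the laboratory, and Table 1 and the monitor's review both fix two times.

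**3. Can the other two rules act?** Yes. A kidney stone can be reported at the week 8 call, where the adverse event log is also marked, and declining cognition can show in the fluency tests given then. So the gap affects two rules of four.

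**4. Exposure without a value**

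- Weeks from dispensing to final visit: 13 − 2 = 11.
- High-dose arm: 11 × 50,000 = 550,000 IU. Comparator: 11 × 5,000 = 55,000 IU.
- If three months is counted as 13 weeks from dispensing: 13 × 50,000 = 650,000 IU and 13 × 5,000 = 65,000 IU.

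**5. How remote is the vitamin D limit?** Entry below 32 means a rise of more than 100 − 32 = 68 ng/mL. Calcium is the rule that matters more.

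**6. How likely is a case?** The documents give no hypercalcemia rate, so the rates below are assumptions. The chance of at least one high-dose participant above 10.5 is 1 − (1 − p)^n, with n = 31 (62 in total) or n = 40 (80 enrolled).

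| Assumed p | n = 31 | n = 40 |
|---|---|---|
| 0.1% | 3% | 4% |
| 0.5% | 14% | 18% |
| 1% | 27% | 33% |
| 2% | 47% | 55% |
| 5% | 80% | 87% |

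The spread shows that the documents cannot settle how often the gap would matter.

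**7. What could be averted?**

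- Symptom check at week 8 with the supplement held at once: up to 13 − 8 = 5 of 11 doses (45%), but only for a participant with symptoms by then.
- Routine week 8 draw acted on at week 9 (one-week turnaround assumed): up to 13 − 9 = 4 of 11 doses (36%), including for a participant without symptoms.
- For that routine draw, assume a persistent excursion with onset uniform over weeks 2 to 13. Mean further time on supplement is 11/2 = 5.5 weeks without the draw. With it, the mean is (6/11) × 4 + (5/11) × 2.5 = 3.32 weeks. Only onsets before week 8, 6/11 or 55% of them, are caught. If excursions cluster late, the gain is smaller.

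**The case against.** The strongest reply is that the wording covers contingencies: any result from any source triggers the rule, including a test ordered by the participant's own provider, whose care is an entry requirement. The risk is also limited by design. Besides hypercalcemia, the protocol excludes GFR below 60, creatinine above 1.2, malabsorption, calcium intake above 1,200 mg a day and, unless known not to be calcium-based, a history of kidney stones. It cites earlier safe use of the dose. The team reviews adverse events weekly, and toxicity symptoms are on its review list. All of this stands. It lowers the likely harm and is a good reason to keep both rules. It does not supply a value during dosing, and weekly or continuing review can only use data that exist.

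A reader might infer several stronger things that the documents do not support:

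- **That the two rules can never act on scheduled data.** The exclusion for hypercalcemia carries no number, and 10.5 is the only calcium threshold given. A week 0 value above it could block dispensing altogether. The supportable statement concerns dosing that has already started.
- **That the week 8 call is the only contact during dosing.** Weekly automated reminder calls also occur, although they are not safety assessments.
- **That the Study Monitoring Criteria fail in the same way.** Those items are counts for team review. Week 13 laboratory values and vital signs can supply them.
- **That a routine interim draw is required.** The protocol says its calcium testing follows published guidelines, which cannot be consulted here, and it gives no event rate from which to show a benefit.

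Up to two pills might remain at week 13 if 13 were dispensed. The bottle is requested at a visit labelled completion, so this does not rescue the rules.

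**Conclusion.** The point holds in a limited form. Two of the four individual stopping rules are written as applying throughout, but no scheduled measurement can trigger them between the first dose and study completion. The interval is about 11 weeks by Table 1, assuming weekly doses from week 2 and full adherence. Week 13 values keep a use: they lead to the repeat laboratory tests and can inform the care of later enrollees. The absolute risk may be low, and nothing in the documents shows that participants will be harmed. The plan should still be corrected, because it states a protection that its schedule does not deliver.

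**What to change.** 1. Keep both limits as stopping triggers, and state that they apply to any result, including unscheduled and outside tests. Removing them from the list would lose that trigger.
2. State in Individual Stopping Criteria that no laboratory value is scheduled between weeks 2 and 13.
3. Add to the week 8 call, and to the handling of any adverse event report, a short check for symptoms of hypercalcemia or vitamin D toxicity. A positive answer prompts an unscheduled calcium and creatinine test sent to the medical monitor, with the supplement held until the result is known.
4. Label the week 13 values as end-of-treatment safety findings, followed by the repeat tests already described in Study Design.

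The cost is a few sentences and an occasional extra test. Even so, an excursion without symptoms would still go unseen until week 13 unless an outside test found it.

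A routine week 8 draw would narrow that gap and remains optional. It costs one extra blood visit and panel for each of 62 to 80 participants. If it included 25-OH D, the result could reveal the arm and would have to go to the medical monitor only, not to those giving the cognitive tests.

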Regarding performance on the *executive functioning* assessments, linear mixed-effects models will be used to estimate the mean change in participants' standardized scores as a function of elapsed time since baseline, treatment assignment, and their interaction. In this study, patients will contribute multiple scores to the analysis and random intercepts will be allowed for each patient to account for their within-subject correlation using an unstructured covariance structure. Regarding model fit, linearity and normality will be assessed using residual and QQ plots, respectively, while outliers will be assessed using box plots. A similar approach will be used to assess performance on assessments of *language and memory* functioning.

Regarding change in *quality of life* and *functioning* self-report measures (i.e., the SAS-SR; SCI-R; PAID; EWPS; PSQI; MOS; and PSS), each participant's baseline score will be subtracted from his/her week 13 score. Subsequently, an independent samples t -

test will be used to compare this change score between participants assigned to the high dose versus those assigned to the low dose. In these comparisons, the distribution of survey scores will be assessed for normality using QQ plots and for outliers using box plots. When survey scores are not normally distributed, an exact version of the Wilcoxon rank-sum test may be used to confirm parametric conclusions.

Finally, summary frequencies will be reported for all reported adverse events during the trial by treatment allocation. This includes the number of affected individuals at risk for the adverse event as well as the number of times the adverse event was reported. All analyses will be completed using SAS version 9.4 (Cary, NC).

Literature Cited

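### The primary cognitive model does not condition on the two pre-dose scores, which costs precision, and its covariance wording leaves the calibration of its test open

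*Combined protocol and SAP*

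**What the plan says.** The Statistical Analysis Plan section models standardized executive-function scores "as a function of elapsed time since baseline, treatment assignment, and their interaction". It adds that "patients will contribute multiple scores to the analysis" and that "random intercepts will be allowed for each patient to account for their within-subject correlation using an unstructured covariance structure". On model checking, "linearity and normality will be assessed using residual and QQ plots, respectively", which points to time as a continuous variable. The section does not list the visits that enter, say which visit is baseline, or use any pre-dose score as a covariate.

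Study Procedures places two full test sessions before dosing. At the second baseline visit "the six cognitive functioning tests will be administered again in order to wash-out any practice effects", and that same visit "will be scheduled to dispense the Vitamin D supplement to the participant". The full battery is next given at three months. In between, at the six-week phone call, participants are "asked about medication compliance and side effects and screening for cognitive function using the Controlled Oral Word Association Test and Animal Naming Test". The schedule ("Table 1: Scheduled Activities") marks cognitive tests at Screening and at Weeks 0, 2, 8 and 13. The primary hypothesis compares the arms at three months.

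**The concern.** Two things are left open.

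- **Use of the pre-dose scores.** The interaction removes chance baseline differences by subtraction. Regression on the pre-dose scores is more precise, and the trial already collects two of them.
- **The covariance matrix.** A single random intercept has one variance, so calling its covariance unstructured adds nothing. Read literally, the within-patient covariance is compound symmetry. The word may instead have been meant for the residual matrix over visits, which is a different model. Under compound symmetry with three visits, the standard error of the treatment-by-time term is right only under particular conditions.

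At stake are the width of the primary interval and, on one reading, the error rate of the primary test.

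**Working it through.** **Inputs.** From Statistical Methods: Power: 31 per arm, SD 15, difference 11, two-sided 5%, stated power 81.1%. From Table 1: full battery at Weeks 0, 2 and 13. The documents give no between-visit correlations and no practice-effect size, so both are assumed. Correlations are written r(0,2)/r(with Week 13). Variances are in units of SD squared.

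**1. The plan's figure.** Noncentrality = (11/15)·√(31/2) = 2.887. The noncentral t with 60 df gives 81.1%, as stated. This compares final scores (variance 1). A change score has variance 2(1−r), which matches only at r = 0.5.

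**2. Weeks 2 and 13 only.** The interaction is the difference in change from Week 2. On one simulated data set the random-intercept fit and the change-score t-test gave the same estimate (−2.063) and standard error (2.872). Simulated type I error was 4.8-5.2%. Variance at r = 0.70 is 2 − 1.40 = 0.60.

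Conditioning on both pre-dose scores, when each correlates r with Week 13, gives 1 − 2r²/(1 + r(0,2)), times (1 + 2/57) for estimating two slopes:
- 0.75/0.70: 1 − 0.98/1.75 = 0.440, giving 0.455 (24% below 0.60)
- 0.85/0.70: 1 − 0.98/1.85 = 0.470, giving 0.487 (19% below 0.60)

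The half-width is 1.96·15·√(2·variance/31): 5.8 points for change, 5.0 and 5.2 for conditioning. Over nine correlation patterns the reduction runs from 12% (r(2,13) = 0.85, others 0.70: 0.265 against 0.300) to 27% (0.65/0.60: 0.583 against 0.800). Simulated type I error when conditioning on both was 4.8-5.2%.

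**3. Weeks 0, 2 and 13, linear time, random intercept only.** Centred times are (−5, −3, 8), with sum of squares 98. The model takes the within-patient variance as s² = 1 − (mean of the three correlations). The true value for the slope is w′Rw/98, with w the centred times and R the correlation matrix. At 0.75/0.70, w′Rw = 98 + 2(15·0.75 − 64·0.70) = 30.9, so the true value is 0.315 against s² = 0.283, a ratio of 1.113.

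A practice jump of J SD common to both arms between Weeks 0 and 2 does not lie on a straight line. Its off-line part, along (11, −13, 2) with squared length 294, is 121J²/294 per patient. It adds 62·(121/294)·J²/122 = 0.209J² to s². Type I error = 2(1 − Φ(1.96/√ratio)):

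| Correlations | True | s², no jump | Ratio, no jump | Type I, no jump | J = 0.4 | J = 0.67 |
|---|---|---|---|---|---|---|
| all 0.70 | 0.300 | 0.300 | 1.000 | 5.0% | 3.9% | 2.5% |
| 0.75/0.70 | 0.315 | 0.283 | 1.113 | 6.3% | 4.9% | 3.2% |
| 0.80/0.70 | 0.331 | 0.267 | 1.240 | 7.8% | 6.2% | 4.1% |
| 0.85/0.70 | 0.346 | 0.250 | 1.384 | 9.6% | 7.6% | 5.1% |
| r(2,13) = 0.85, others 0.70 | 0.227 | 0.250 | 0.906 | 4.0% | 2.8% | 1.6% |

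Simulations with 31 per arm agreed to within about 0.3 percentage points.

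On the Week 13 scale, where an effect present only at Week 13 moves the slope by 8/98, this estimator has variance w′Rw/64: 0.483 at 0.75/0.70 and 0.530 at 0.85/0.70. Those are half-widths of 5.2 and 5.4 points. With no jump the model would report 4.9 and 4.6.

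**4. Residual matrix unstructured.** The standard error is correct. With visit categorical, arm means free and complete data, the Week 13 minus Week 2 contrast is again the change score, with the precision in step 2.

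**5. Power for 11 points at r = 0.70 (normal approximation).** Change from Week 2: 96.1%. Conditioning on both: 98.5% at 0.85/0.70. At lower correlations the gap is wider: with r = 0.5 to Week 13 and 0.9 between the pre-dose scores, 81.1% against 91.1%.

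**The case against.** A reader might infer that the primary test is anti-conservative, with a false-positive rate near 10%. The documents do not support that. Inflation needs all of these together: both pre-dose visits in the model, linear time, no unstructured residual matrix, pre-dose scores that correlate more with each other than with Week 13, and little practice effect. The plan states none of them. It uses the word unstructured, which may well refer to the residual matrix, and then the standard error is right. It also expects practice effects, since the second battery is there to wash them out. Under linear time a common jump of 0.4 SD removes the inflation at 0.75/0.70, and one of 0.67 SD removes it even at 0.85/0.70. With equal correlations the test becomes conservative. All of this stands. What remains is that the error rate on that reading depends on quantities the plan does not control.

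It can also be said that a change-score comparison is valid, and that preferring regression adjustment is a matter of efficiency. That too is correct. The gain is 0.6-0.8 points of half-width against change from Week 2, and about 0.2 against the three-visit slope, beside an 11-point target difference. But the second pre-dose score is already being collected and paid for.

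**Conclusion.** The point holds as a precision and specification issue. The planned model does not condition on the Week 0 and Week 2 scores. Relative to change from Week 2, doing so lowers the variance by 12-27% over the patterns tried. At a correlation of 0.70 with Week 13 that is mainly interval width; at about 0.5 it is also a visible gain in power.

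The plan's wording admits three analyses: a valid change-score test, a model with a correct standard error from an unstructured residual matrix, and a random-intercept slope whose error rate is about 4-10% with no practice effect and lower with one. Nothing here shows that the trial is invalid or its sample size wrong.

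The figures rest on assumed correlations and jump sizes, equal variances across visits and complete data at 31 per arm. With dropout (80 enrolled to obtain 62), validity also needs data missing at random and an adequate covariance model.

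**What to change.** Name the Week 13 between-arm difference as the primary contrast, list the visits that enter, and condition on both pre-dose scores by one stated model:

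1. For tests given at Weeks 0, 2 and 13: ANCOVA of the Week 13 score on treatment, Week 0 score and Week 2 score.
2. Alternatively, where incomplete data are to be kept or a Week 8 score exists (Controlled Oral Word Association, Animal Naming): categorical visit, arm means constrained equal at Weeks 0 and 2, treatment-by-visit after dosing, unstructured residual covariance without a random intercept, and Kenward-Roger degrees of freedom.

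For the two fluency tests, also say whether the phone scores at screening and Week 8 are used.

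The cost is SAP wording and a few lines of SAS, with no new data. Model 1 spends two covariate degrees of freedom. Against a random-intercept model (2 covariance parameters), model 2 has 6 with three visits and 10 with four, so 4 or 8 more. Little is at risk if compound symmetry is true: at 0.70 throughout, the variance is 0.44 conditioning on both scores (slopes estimated) against 29.4/64 = 0.46 for the literal slope. The simulated error rates in the working cover model 1 only; model 2 was not simulated.
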